6.3.2.1. Patient Global Impression of Change – Hemophilia (PGIC-H)

PGIC-H response will be summarized as categorical variable. The response scale is a 7-point categorical response centered on 'no change' with 3 grades of improvement and 3 grades of worsening. If the number is too small for a category, the response to PGIC-H 'greatly improved' and 'moderately improved' will be combined into a category of 'at least moderately improved'. And the response of PGIC-H 'greatly worsened' and 'moderately worsened' will be combined into a category of 'at least moderately worsened' will be combined into a category of 'at least moderately worsened'. In the summary table, the number of total non-missing observations, and frequencies, the proportion of participants in each of response category will be presented by study visit. The Dosed population will be used for this analysis.

6.3.2.2. Hemophilia Life Impacts Questionnaire (HLIQ)

The HLIQ is a 9-item assessment of life impacts associated with living with and treating hemophilia. Number and percentage of participants within each response category will be summarized for each question by study visit. The Dosed population will be used for this analysis.

6.3.2.3. EQ-5D-5L

The number and percentage of participants in each level of the 5 dimensions of health score will be assessed and summarized by visit. The VAS score and the Index score (total score) will be compared to its own baseline using paired t-test. The n, median, Q1, Q3, minimum, maximum, mean and standard deviation, the 95% confidence limits of actual value and the change from baseline will be summarized in the table. The Dosed population will be used for this analysis.

6.3.3. Vector Shedding

Descriptive summaries of shedding vector levels in PBMC, saliva, urine, semen and plasma will be provided, including a summary of peak levels and time to peak levels. If multiple assessments are collected for a study visit, the largest value will be included in the summary as a conservative approach. Number and percentage of participants with BLoQ value at each visit will also be summarized in the table. A mean \pm standard error plot of vector shedding over time will be generated with specimen types differentiated by different color/symbols. In the descriptive summary table and the Mean \pm SE plot, only values with assessments above LLQ will be included. In these tables and figures, results from samples without DNase treatment will be presented. The figures will be presented in log-linear scales.

For a subset of participants in C0371002, samples will also be assessed by DNase digestion method for saliva, semen and urine. For these samples, results from both Dnase-digested and DNase undigested samples will be summarized separately in another table, with columns representing the lab method. Individual plots of vector shedding over time will be generated for all participants in the Dosed population. The plot will be paged by participant and paneled by specimen type, and results from both lab methods will be plotted on the same figure, differentiated by color/symbols. In the individual plot, BLoQ value will be imputed as one half of the LLQ value for plotting purposes. Results from the two methods will be presented side by side in a data listing.

Time to undetectable vector (defined as time to first of three consecutive negative results), time to last of three consecutive negative results, and time to the last positive prior to three consecutive negative will be summarized. The summary table will be generated for the 'Vector Shedding substudy' population and the Dosed population.

Vector Shedding subgroup will have more extensive vector shedding analysis performed on their specimens to further characterize the kinetics of vector shedding. The data of this subgroup will be separately presented.

6.3.4. FIX Antigen Levels and Coagulation Activation Tests

The n, mean, median, Q1, Q3 and range will be presented in the summary tables for FIX antigen levels and coagulation activation tests as specified in Section 3.3.4.

6.4. Subset Analyses

No subset analysis is planned for this study.

6.5. Baseline and Other Summaries and Analyses

6.5.1. Baseline Summaries

Demographic information, baseline characteristics of Dosed population will be summarized. Medical history/Hemophilia history data at study entry, including information collected in the lead-in study (C0371004) will also be summarized.

6.5.2. Study Conduct and Subject Disposition

Participant disposition will be summarized for the Enrolled population. This table will present the count and percentage of participants in each disposition category: number discontinued and reason for discontinuation (including number of screen failure), number completed, and number ongoing. A data listing will be provided along the disposition table.

6.5.3. Study Treatment Exposure

PF-06838435 infusion information will be summarized in the Dosed population. Duration of infusion, and total dose of PF-06838435 (in vector genomes [vg] and vector genomes per kilogram [vg/kg]), whether actual dose was adjusted from planned will be summarized.

6.5.4. Concomitant Medications and Nondrug Treatments

Concomitant medication other than FIX replacement infusions and non-drug treatment will be summarized. Concomitant medication associated with AE will be summarized since these concomitant medications will be collected from Year 2 through Year 6.

6.6. Safety Summaries and Analyses

All safety analyses, including analyses of AEs, clinical laboratory results, vital signs, and physical examinations will be conducted on the 'Safety' analysis population. In this study, 'Safety' population is the same as Dosed population.

6.6.1. Adverse Events

An overall table summarizing AEs reported during the entire study will be sorted by system organ class and preferred term. Per protocol, adverse events assessed as non-serious and unrelated to study drug are reported within the first year post infusion only and not subject to reporting thereafter. As a consequence, the all-causality TEAE tables will include a footnote to convey non-serious unrelated AE were collected over the initial year and not the subsequent 5-year study duration for a given participant.

All AEs occurring during the first year (up to and including 52 weeks post PF-06838435 infusion) will be summarized, sorted by system organ class and preferred term. All AE summary tables will be generated to display all AEs, relationship to study drug, severity of the AE ('Mild', 'Moderate', and 'Severe'), and if serious AE or not.

All serious AEs, treatment-related non-serious AEs, AESIs, AE leading to study discontinuation, and AE leading to death will be summarized per Pfizer Data Reporting Standard, for AE reported during short term (up to and 52 weeks post PF-06838435 infusion)

and AE reported during the entire course of study including long-term monitoring (post PF-06838435 infusion to Year 6 or EOS), respectively.

6.6.2. Laboratory Data

Safety laboratory tests and other laboratory tests specified in Section 3.5.2 will be summarized descriptively by study visits.

Categorical shift of abnormal to normal, or normal to abnormal, of selected lab tests will be summarized. These lab tests are LFT, α -Fetoprotein, hematology, and clinical chemistry parameters.

LFT measures consist of protocol-specified tests, including AST, ALT, Gamma-glutamyl transpeptidase (GGT) and Lactate dehydrogenase (LDH) etc.. Baseline and post-baseline visits will be summarized with descriptive statistics by visit and will be presented in a data listing. Number of participants (n), mean, standard deviation (SD), median, Q1, Q3, minimum and maximum will be presented for all change from baseline tables. Each participant's laboratory values will be classified according to whether the test result is "low" (i.e., below the lower limit of normal [LLN]), "normal" (within the normal range), or "high" (i.e., above the upper limit of normal [ULN]). The abnormality categorical data will be summarized in shift tables comparing the results at the end of study visit, minimum post-baseline, and maximum post-baseline with those at the baseline visit.

The number and percentage of participants with corticosteroid treatment, with corticosteroid dose escalation before weaning, with corticosteroid dose escalation during weaning will be provided in addition to a summary of time to corticosteroid initiation, time from corticosteroid initiation to first wean of corticosteroid, time from corticosteroid initiation to first corticosteroid escalation, total dose and total time on corticosteroid. Total time on corticosteroid is calculated as (date of stopping of corticosteroid treatment. For summaries of corticosteroid dose escalation and dose escalation during weaning, the denominator will be the number of participants with corticosteroid treatment.

6.6.3. Vital Signs/Physical Examination/Other Safety Outcome

Vital signs, electrocardiograms, and physical examination will be summarized per Pfizer Data Reporting Standard. Any abnormal findings from liver ultrasound will be listed.

6.7. COVID-19 Related Data Listings and Summaries

The impact of Coronavirus disease 2019 (COVID-19) on C0371002 is expected to be minimal. While there was a pause in dosing new participants, since no more than the single dose of PF-06838435 infusion on Day 1 will be administered during the study, there should be no treatment discontinuations. Additionally given the mechanism of data collection for key endpoints (i.e. eDiary to capture bleeding and infusion information and the availability of mobile phlebotomy/home health services to collect blood samples) missing data due to COVID-19 is expected to be minimal for the primary endpoint (ABR_{total}) and the key

secondary endpoints (AIR, ABR_{treat} and FIX:C). Additionally, it is not anticipated that participants would discontinue from the study due to COVID-19. To confirm that COVID-19 has not impacted the trial, the following data listings and summaries will be provided.

- Study disruption/discontinuation due to COVID-19 will be listed, and a description of how the individual's participation was altered will be provided.
- Protocol Deviations related to COVID-19 will be listed.
- Missed Visits/Data for FIX:C due to COVID-19 will be listed.
- COVID-19 related Adverse Events will be summarized by system organ class and preferred term, and will also be listed.
- Any study discontinuation due to COVID-19 related AE, SAE or death related to COVID-19 will be listed.

7. INTERIM ANALYSES

7.1. Introduction

There is no interim analysis planned for this study. As this study is an open-label study, the sponsor may conduct unblinded reviews of the data during the course of the study for the purpose of safety assessment.

8. APPENDIX

Appendix 1. Statistical Methodology Details

Appendix 1.1. Example of SAS Code of Repeated Measure Additive Negative Binomial Regression Model:

proc genmod data=alldata;

class trt subjid;

model bleeds = years years*trt/link=identity dist=negbin noint;

repeated subject=subjid/Type=UN;

estimate 'diff' years*trt 1 -1/alpha=0.05; * adjust the alpha to a level if needed.

Estimate 'Prophy' years 1 years*trt 0 1;

estimate 'GTx' years 1 years*trt 1 0;

run;

Appendix 1.2. Example of SAS Code of Repeated Measure Negative Binomial Regression Model with log link:

```
proc genmod data=allbdyr; (offset=natural log of years)
    class trt subjid;
    model bleeds = trt /offset=lyears dist=negbin link=log alpha=0.05; * adjust the alpha to a
level if needed.
```

Repeated subject=subjid/ Type=UN; estimate 'log diff' trt 1 -1 / exp; ods output estimate=ci ratio;

run;

data ci_reduction;

set ci_ratio;

where Label= "Exp(log diff)";

Percent_reduction = 1- LbetaEstimate ;

```
Lower_bound = 1- LbetaUpperCL;
```

```
Upper_bound = 1- LbetaLowerCL;
```

Run;

Abbreviation	Term
AAV	Adeno-associated virus
ABR	annualized bleeding rate
ADA	anti-drug antibody
AE	adverse event
AESI	adverse event of special interest
AIR	annualized (FIX) infusion rate
ALT	alanine transaminase
APRI	AST to platelet ratio index
aPTT	activated partial thromboplastin time
AST	aspartate transaminase
BLoQ	Below limit of quantification
BUN	blood urea nitrogen
CDF	cumulative distribution functions
CI	confidence interval
COVID-19	Coronavirus disease 2019
CRF	case report form
CSR	clinical study report
DNA	deoxyribonucleic acid
DNase	deoxyribonuclease
ECG	electrocardiography
EHL	extended half-life
ELISPOT	enzyme-linked immunosorbent spot
EOS	end of study
EQ-5D-5L	EuroQoL, 5-dimensions, 5-levels
FIX	Factor IX
FIX:C	Factor IX: circulating
GGT	gamma-glutamyl transpeptidase
Haem-A-QoL	Haemophilia Quality of Life Questionnaire for Adults
HAL	Haemophilia Activities List
HBV	hepatitis B virus
HBcAb	hepatitis B core antibody
HBsAg	hepatitis B surface antigen
HCV	hepatitis C virus
hFIX-Padua	human factor IX-Padua
HIV	human immunodeficiency virus
HJHS	Hemophilia Joint Health Score
HLIQ	Hemophilia Life Impacts Questionnaire
IA	interim analysis
ICF	informed consent Form
IFNγ	interferon gamma

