## 9.2. Sample Size Determination

Participants who complete the lead-in protocol C0371004 will be screened to achieve desired sample size of 40 participants, and eligible participants will be assigned to study intervention. All 40 participants are expected to be evaluable in this one-armed study.

When all 40 participants have completed at least 15 months of follow-up post-infusion of PF-06838435, the  $ABR_{total}$  data will provide at least 90% power (one-sided test with  $\alpha=0.025$ ) to demonstrate non-inferiority of gene therapy compared to prophylaxis treatment on the difference in  $ABR_{total}$ , using a repeated measure negative binomial regression, with a non-inferiority margin of 3.0 bleeds/year. The assumed background rate of annualized bleeding is a conservative 5.0 and the assumed annualized bleeding rate post-PF-06838435 is 1.5. The details of non-inferiority margin selection are included in [Appendix 10](#).

The number of participants may exceed 40, because all participants who complete the lead-in study (C0371004) and meet other eligibility criteria will be allowed to participate in this study.

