## 9.4. Statistical Analyses

The SAP will be developed and finalized before database lock and will describe the participant populations to be included in the analyses, any multiple testing procedures (to control the overall type I error of primary, secondary hypothesis test), and procedures for accounting for missing, unused, and spurious data. The overall probability of Type 1 error alpha for primary statistical tests, and other tests included in the multiple testing procedure, is controlled at .05 (or one-sided .025). Any minor changes to the statistical methodology stated in the protocol will be described in the SAP. This section is a summary of the planned statistical analyses of the primary and secondary endpoints.

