6. ANALYSES AND SUMMARIES

6.1. Primary Endpoint(s)

6.1.1. ABR for Total Bleeds

6.1.1.1. Main Analysis

ABR_{total} will be analyzed using a repeated measures generalized linear model with negative binomial distribution and identity link function. Treatment (prophylaxis, or PF-06838435) and duration will be included in the model. Treatment will be a class factor in the model, duration is numeric and participant will be a random effect. Duration is the elapsed time in years of each treatment period. Duration is at least 0.5 for pre-PF-06838435 infusion prophylaxis which corresponds to six months. This period begins at enrollment of the lead-in study and ends on date of PF-06838435 infusion. Duration of PF-06838435 period is the observed time from Week 12 (Day 82) until cutoff for the specified analysis (e.g. 15 months for the primary analysis) or the date of study withdrawal or resumption of FIX infusion (whichever is earlier), minus any time that is predefined to be excluded.

- The Dosed population will be the primary analysis population. Analysis will be repeated for the Evaluable population if it is different from Dosed population.
- The mean ABR_{total} from Week 12 to Month 15 will be compared to the pre-infusion mean via the estimation of the mean difference and 95% CI. If the upper bound of the confidence interval of the difference of (ABR_{total} PF-06838435 ABR_{total} FIX prophylaxis) is smaller than 3.0, then statistical significance of the noninferiority claim would be demonstrated. An example of SAS code of such analysis is included in the Appendix 1.1. If noninferiority is demonstrated, further testing for superiority would be conducted after the primary analysis (assuming other endpoints within the

testing hierarchy are statistically significant), using the same method, except the margin would be modified to 0.

• The summary table will include two columns, for FIX prophylaxis and PF-06838435, respectively. The summary statistics in the table will include n, mean, median, Q1, Q3, range of the observed ABR_{total}, model derived mean ABR_{total} and 95% CI, estimated mean difference (model derived), and the 95% CI of the mean difference (model derived).

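### The SAP describes the primary model as random-effects but codes it as a GEE, and with 40 participants the coded interval's one-sided error at the non-inferiority boundary exceeds the stated 0.025

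*SAP*

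**What the plan says.** **Model in the text.** SAP 6.1.1.1 describes a repeated measures negative binomial model with identity link, in which treatment is a class factor and "participant will be a random effect". The distribution and scale of that random effect are not given.

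**Model in the code.** The same section points to SAP Appendix 1.1 for example code. The code is PROC GENMOD with the line "repeated subject=subjid/Type=UN" and no random-effect statement. No small-sample option is requested.

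**Decision rule.** If the upper 95% confidence limit of the post-minus-pre difference in ABR_total "is smaller than 3.0, then statistical significance of the noninferiority claim would be demonstrated".

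**Error rate.** Protocol 9.4 says that the overall type 1 error "is controlled at .05 (or one-sided .025"). Protocol 9.2 plans a one-sided 0.025 test.

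**Planning figures (Protocol 9.2).** The data "will provide at least 90% power" "with a non-inferiority margin of 3.0 bleeds/year". On rates: "The assumed background rate of annualized bleeding is a conservative 5.0 and the assumed annualized bleeding rate post-PF-06838435 is 1.5". On numbers: "All 40 participants are expected to be evaluable in this one-armed study". The section adds that enrolment may exceed 40.

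**Reuse.** SAP 6.2.1 and 6.2.5 apply the same method to ABR_treat and to the bleed subtypes. SAP Table 2 tests these for non-inferiority in the gatekeeping sequence.

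**The concern.** The text and the code cannot both be followed. A REPEATED statement in GENMOD fits a marginal model by estimating equations, and it reports limits based on an empirical (sandwich) standard error. A participant random effect defines a different likelihood and a different standard error. One confidence limit compared with 3.0 decides the primary objective and opens the testing sequence, so the analyst should not have to choose between the two.

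The coded version also has a known small-sample weakness. The uncorrected sandwich variance divides by n rather than n-1, and the limit uses a normal rather than a t quantile. With 40 clusters both features shorten the interval. At the non-inferiority boundary, the right-skewed bleed counts shorten it further on the side that matters. Neither document mentions a small-sample correction, a t reference, a bootstrap or a simulated error rate.

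**Working it through.** **Inputs from the documents.** n = 40; one-sided 0.025; margin 3.0; rates 5.0 and 1.5 (Protocol 9.2). Pre-infusion duration at least 0.5 year (SAP 6.1.1.1). Post-infusion window Day 82 to Day 469 = 388 days = 1.062 years (SAP 5.2).

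**Assumed, because the documents give neither:** negative binomial dispersion k and the pre/post correlation.

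**1. The plan's power figure.** The planned difference is 1.5 - 5.0 = -3.5, and its distance to the margin is 3.0 - (-3.5) = 6.5. For 90% power, SE must be at most 6.5/(1.960 + 1.282) = 2.005, so the SD of the paired difference must be at most 2.005 x sqrt(40) = 12.68. The variance is rate/T + k x rate² in each period. With no correlation and a half-year pre-period:
- k = 4: (10 + 100) + (1.41 + 9) = 120.4, SE = 1.735, power about 96%.
- k = 6: (10 + 150) + (1.41 + 13.5) = 174.9, SE = 2.091, power about 87%.

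The 90% claim is therefore plausible over a wide range of k. It cannot be reproduced exactly without the plan's own k.

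**2. Normal theory.** If all participants have the same exposure within a period, the coded estimate is the mean paired difference, with an n-divisor variance. Non-inferiority is declared when the usual t statistic is below -1.960 x sqrt(39/40) = -1.935. For exactly normal differences P(t39 < -1.935) = 0.0301. With n = 45 the same calculation gives 0.0295.

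**3. Bleed counts at the boundary.** One-sided error of the coded upper limit, n = 40, true difference 3.0:

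| Setting | Error |
|---|---|
| Poisson counts, equal exposures, half-year pre-period, 40,000 trials per scenario | 0.027-0.030 |
| Same, k = 0.25-2 | 0.033-0.082 |
| Identity-link GEE with estimated correlation, 5.0 vs 8.0, k = 0.5-4, pre-period 0.5-1.5 years, 20,000 trials per scenario | 0.035-0.113 |

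Every boundary scenario exceeded 0.025. With n = 45 and half-shared frailty the error was 0.043 (k = 1) and 0.053 (k = 2).

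**4. Away from the boundary.** At 5.0 vs 1.5 the upper limit fell below the true difference in 0.008-0.024 of trials (equal exposures). In a GEE simulation with k = 0.5-3 it did so in 0.005-0.015. For superiority (true difference 0, margin 0) the error was 0.021-0.032.

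**5. Does the choice of model matter?** As an illustration, a shared gamma frailty model was fitted by maximum likelihood (5.0 vs 8.0, k = 1 and 2, 1,200 trials each). Likelihood-ratio error was 0.028-0.034 when the frailty was fully shared between periods and 0.15-0.19 when half was shared. The model-based Wald errors were 0.048-0.063 and 0.18-0.23. The SAP does not say which random effect it means, so these figures show sensitivity to the choice and are not the error of the plan.

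**6. Effect of a correction.** Mancl-DeRouen with t39 gave 0.020-0.072 in the equal-exposure runs of step 3 and 0.028-0.103 in the wider GEE grid. The change in width with equal exposures follows from t39/z = 2.023/1.960 = 1.032:
- Kauermann-Carroll: sqrt(40/39) x 1.032 = 1.045.
- Mancl-DeRouen: (40/39) x 1.032 = 1.058.

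Power at 5.0 vs 1.5 stayed at or above 0.966 with Mancl-DeRouen and t39, for k up to 6.

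**The case against.** The code is labelled an example, and the sandwich standard error and normal quantile are software defaults rather than SAP wording. Asymptotic Wald limits are common practice, and the Protocol's one-sided 0.025 can be read as a nominal level. The Protocol's term for the model, a repeated measure negative binomial regression, fits a GEE. All of this is fair, but the code is the only operational specification, and it still contradicts the text.

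The size of the excess depends on assumptions. Without overdispersion it is only 0.027-0.030, and anything larger rests on an assumed k. That stands, and it is why ranges are given.

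A reader might also note that two-sided coverage at the planning rates is only 0.90-0.94 in simulation (k = 0.5-3) and infer that the primary decision is compromised there. That inference fails. The decision uses the upper limit alone, and step 4 shows that limit to be conservative at those rates. The shortfall is in the lower limit (0.050-0.097), which does not enter the non-inferiority rule.

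Finally, the usual correction does not restore 0.025 once counts are overdispersed. That also stands, so the correction should come with simulated error rates rather than be presented as a cure.

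**Conclusion.** The conflict between SAP 6.1.1.1 and Appendix 1.1 is plain on the page and does not depend on any assumption. As coded, with GENMOD defaults and 40 participants, the non-inferiority test has a one-sided error at the boundary of about 0.030 under normal theory, 0.027-0.030 for Poisson counts, and about 0.033-0.08 for assumed dispersion 0.25-2. The direction was the same in every boundary scenario run; the amount depends on dispersion, correlation and pre-period length.

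A reader might infer that the trial is likely to declare non-inferiority falsely, or that its power is overstated. The documents do not support that. If the planning rates hold, the true difference is 6.5 bleeds/year inside the margin and the conclusion is unlikely to change. Superiority testing is also close to nominal. The defect is an unreconciled primary model and an error rate that is stated but not delivered at the margin.

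**What to change.** 1. Name one model. Either delete the random-effect wording in SAP 6.1.1.1 and name the GEE, or change the Appendix 1.1 code to match the text and specify the random effect. Align the same wording in SAP 6.1.1.2 and Appendix 1.2.
2. If the GEE is kept, base the primary confidence interval on a bias-corrected sandwich standard error (Mancl-DeRouen or Kauermann-Carroll) with t on n-1 degrees of freedom. Apply it to ABR_total, ABR_treat and the bleed subtypes.
3. Report the simulated one-sided error at the 3.0 margin over a stated range of dispersion and pre/post correlation.
4. Add a participant-level bootstrap-t interval as a sensitivity analysis. In 1,500 trials per scenario its boundary error was 0.027-0.059, so it is not exact either.
5. State that the correction reduces but does not remove the skewness-driven excess at higher dispersion.

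The cost is SAP wording, code and one simulation. The interval becomes about 4.5-6% wider, and the planned power of at least 90% still holds at the planning rates over the dispersions simulated (k up to 6).
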